## **Appendix 1** **Schedule of Assessments (cont.)**

- p. After informed consent has been obtained, but prior to initiation of study drug, only SAEs caused by a protocol-mandated intervention should be reported. After initiation of study drug, all SAEs and AEs of special interest, regardless of relationship to study drug, will be reported until 90 days after the last dose of study drug or initiation of new anti-cancer therapy, whichever occurs first. All other AEs, regardless of relationship to study drug, will be reported until 30 days after the last dose of study drug or initiation of new anti-cancer therapy, whichever occurs first. After this period, the investigator should report any SAEs or AEs of special interest believed to be related to prior study drug treatment. The investigator should follow each AE until the event has resolved to baseline grade or better, the event is assessed as stable by the investigator, the patient is lost to follow-up, or the patient withdraws consent. Every effort should be made to follow all SAEs considered to be related to study drug or study-related procedures until a final outcome can be reported.
- q. Survival and new anti-cancer therapy follow-up information will be collected via telephone contact, patient medical records, and/or clinic visits approximately every 3 months until death, loss to follow-up, end of study, patient withdrawal or study termination by the Sponsor, whichever occurs first.

## **Appendix 2** **Modified Response Evaluation Criteria in Solid Tumors**

Conventional response criteria may not be adequate to characterize the anti-tumor activity of immunotherapeutic agents like atezolizumab, which can produce delayed responses that may be preceded by initial apparent radiological progression, including the appearance of new lesions. Therefore, modified response criteria have been developed that account for the possible appearance of new lesions and allow radiological progression to be confirmed at a subsequent assessment.

Modified Response Evaluation Criteria in Solid Tumors (RECIST) is derived from RECIST, Version 1.1 (RECIST v1.1) conventions and immune-related response criteria (irRC). When not otherwise specified, RECIST v1.1 conventions will apply.

### **Modified RECIST and RECIST, Version 1.1: Summary of Changes**

	RECIST v1.1	Modified RECIST
New lesions after baseline	Define progression.	New measurable lesions are added into the total tumor burden and followed.
Nontarget lesions	May contribute to the designation of overall progression	Contribute only in the assessment of a complete response
Radiographic progression	First instance of $\geq 20\%$ increase in the sum of diameters or unequivocal progression in nontarget disease	Determined only on the basis of measurable disease; may be confirmed by a consecutive assessment $\geq 4$ weeks from the date first documented

RECIST = Response Evaluation Criteria in Solid Tumors.

### **DEFINITIONS OF MEASURABLE/NONMEASURABLE LESIONS**

All measurable and nonmeasurable lesions should be assessed at screening and at the protocol-specified tumor assessment timepoints. Additional assessments may be

---

## **Appendix 2** **Modified Response Evaluation Criteria in Solid Tumors (cont.)**

performed, as clinically indicated for suspicion of progression. The investigator will evaluate response to treatment with use of modified RECIST.

### **MEASURABLE LESIONS**

**Tumor Lesions.** Tumor lesions must be accurately measured in at least one dimension (longest diameter in the plane of measurement is to be recorded) with a minimum size as follows:

- 10 mm by computed tomography (CT) or magnetic resonance imaging (MRI) scan (CT/MRI scan slice thickness/interval no greater than 5 mm)
- 10-mm caliper measurement by clinical examination (lesions that cannot be accurately measured with calipers should be recorded as nonmeasurable)

**Malignant Lymph Nodes.** To be considered pathologically enlarged and measurable, a lymph node must be  $\geq 15$  mm in the short axis when assessed by CT scan (CT scan slice thickness recommended to be no greater than 5 mm). At baseline and follow-up, only the short axis will be measured and followed.

### **NONMEASURABLE LESIONS**

Nonmeasurable tumor lesions encompass small lesions (longest diameter  $< 10$  mm or pathological lymph nodes with short axis  $\geq 10$  but  $< 15$  mm), as well as truly nonmeasurable lesions. Lesions considered truly nonmeasurable include leptomeningeal disease, ascites, pleural or pericardial effusion, inflammatory breast disease, lymphangitic involvement of skin or lung, peritoneal spread, and abdominal mass/abdominal organomegaly identified by physical examination that is not measurable by reproducible imaging techniques.

### **SPECIAL CONSIDERATIONS REGARDING LESION MEASURABILITY**

Bone lesions, cystic lesions, and lesions previously treated with local therapy require particular comment, as outlined below.

### **BONE LESIONS**

Bone scan, positron emission tomography (PET) scan, or plain films are not considered adequate imaging techniques for measuring bone lesions. However, these techniques can be used to confirm the presence or disappearance of bone lesions.

Lytic bone lesions or mixed lytic–blastic lesions, with identifiable soft tissue components, that can be evaluated by cross-sectional imaging techniques such as CT or MRI can be considered as measurable lesions if the soft tissue component meets the definition of measurability described above.

## **Appendix 2** **Modified Response Evaluation Criteria in Solid Tumors (cont.)**

Blastic bone lesions are nonmeasurable.

### **CYSTIC LESIONS**

Lesions that meet the criteria for radiographically defined simple cysts should not be considered as malignant lesions (neither measurable nor nonmeasurable) since they are, by definition, simple cysts.

Cystic lesions thought to represent cystic metastases can be considered as measurable lesions, if they meet the definition of measurability described above. However, if noncystic lesions are present in the same patient, these are preferred for selection as target lesions.

### **LESIONS WITH PRIOR LOCAL TREATMENT**

Tumor lesions situated in a previously irradiated area or in an area subjected to other loco-regional therapy are usually not considered measurable unless there has been demonstrated progression in the lesion. Study protocols should detail the conditions under which such lesions would be considered measurable.

### **TUMOR RESPONSE EVALUATION**

#### **DEFINITIONS OF TARGET/NONTARGET LESIONS**

##### **Target Lesions**

When more than one measurable lesion is present at baseline, all lesions up to a maximum of five lesions total (and a maximum of two lesions per organ) representative of all involved organs should be identified as target lesions and will be recorded and measured at baseline. This means that, for instances in which patients have only one or two organ sites involved, a maximum of two lesions (one site) and four lesions (two sites), respectively, will be recorded. Other lesions (albeit measurable) in those organs will be recorded as nonmeasurable lesions (even if the size is  $> 10$  mm by CT scan).

Target lesions should be selected on the basis of their size (lesions with the longest diameter) and be representative of all involved organs, but in addition, should lend themselves to reproducible repeated measurements. It may be the case that, on occasion, the largest lesion does not lend itself to reproducible measurement, in which circumstance, the next largest lesion that can be measured reproducibly should be selected.

Lymph nodes merit special mention since they are normal anatomical structures that may be visible by imaging even if not involved by tumor. As noted above, pathological nodes that are defined as measurable and may be identified as target lesions must meet the criterion of a short axis of  $\geq 15$  mm by CT scan. Only the short

## **Appendix 2** **Modified Response Evaluation Criteria in Solid Tumors (cont.)**

axis of these nodes will contribute to the baseline sum. The short axis of the node is the diameter normally used by radiologists to judge if a node is involved by solid tumor. Nodal size is normally reported as two dimensions in the plane in which the image is obtained (for CT, this is almost always the axial plane; for MRI, the plane of acquisition may be axial, sagittal, or coronal). The smaller of these measures is the short axis. For example, an abdominal node that is reported as being 20 mm  $\times$  30 mm has a short axis of 20 mm and qualifies as a malignant, measurable node. In this example, 20 mm should be recorded as the node measurement. All other pathological nodes (those with short axis  $\geq$  10 mm but  $<$  15 mm) should be considered nontarget lesions. Nodes that have a short axis of  $<$  10 mm are considered non-pathological and should not be recorded or followed.

Lesions irradiated within 3 weeks prior to Cycle 1, Day 1 may not be counted as target lesions.

### **Nontarget Lesions**

All other lesions (or sites of disease), including pathological lymph nodes, should be identified as nontarget lesions and should also be recorded at baseline. Measurements are not required.

It is possible to record multiple nontarget lesions involving the same organ as a single item on the Case Report Form (CRF) (e.g., “multiple enlarged pelvic lymph nodes” or “multiple liver metastases”).

After baseline, changes in nontarget lesions will contribute only in the assessment of complete response (i.e., a complete response is attained only with the complete disappearance of all tumor lesions, including nontarget lesions) and will not be used to assess progressive disease.

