#### **4.1.1 Inclusion Criteria**

Patients must meet the following criteria for study entry:

1. Signed informed consent form
2. Age  $\geq$  18 years
3. Is, according to the investigator's judgment, able to comply with the study protocol
4. Histologically documented locally advanced (T4b, any N; or any T, N 2–3) or metastatic (M1, Stage IV) urothelial or non-urothelial carcinoma of the urinary tract
  - Urinary tract carcinoma includes carcinoma of the bladder, ureter, urethra, and renal pelvis
  - Primary non-urothelial carcinoma includes all sub-types listed in the WHO classification (see [Appendix 8](#))
    - Bellini collecting duct tumors are allowed if independently reviewed by two expert pathologists from different sites
    - Lymphoma, sarcoma, and renal cell carcinoma are excluded
5. Patients with measurable and/or non-measurable disease according to RECIST v1.1 are allowed
6. Must have progressed during or following treatment with at least one (and not more than 3) prior treatments for inoperable, locally advanced or metastatic urothelial or non-urothelial carcinoma of the urinary tract
  - Patients who received prior adjuvant/neoadjuvant chemotherapy and progressed within 12 months of treatment will be considered as having a first line of treatment for metastatic disease
  - Patients who were intolerant to prior systemic treatment are allowed as long as they had received at least 2 treatment cycles
  - Platinum- or non-platinum-based chemotherapy regimens are allowed
  - Low-dose chemotherapy given as radiosensitizer for curative treatment of localized disease does not count as a line of systemic chemotherapy
7. Representative formalin-fixed paraffin-embedded (FFPE) tumor specimen block available for submission.

- Only tissue from core needle (with  $\geq$  3 cores), punch, incisional, excisional, or forceps biopsies will be accepted. Fine-needle aspiration, brushing, bone tissue, and lavage samples are not acceptable
- If an appropriate tumor specimen is not available, a sample will be collected by biopsy during the study screening period
- ONLY at sites where local laws and regulations prohibit the sending of tumor specimen blocks to an outside central laboratory, specimen slides are acceptable. A minimum of 15 unstained serially-cut sections must be prepared and sent per tumor sample. For details, please refer to the Sample Handling Manual

8. Eastern Cooperative Oncology Group (ECOG) Performance Status 0, 1 or 2

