## **Appendix 2** **Modified Response Evaluation Criteria in Solid Tumors (cont.)**

### **RESPONSE CRITERIA**

#### **Evaluation of Target Lesions**

**Complete Response (CR):** Disappearance of all target lesions. Lymph nodes that shrink to < 10 mm short axis are considered normal.

**Partial Response (PR):** At least a 30% decrease in the sum of the diameters of all target and all new measurable lesions, taking as reference the baseline sum of diameters, in the absence of CR.

**Note:** The appearance of new measurable lesions is factored into the overall tumor burden but does not automatically qualify as progressive disease until the sum of the diameters increases by  $\geq 20\%$  when compared with the sum of the diameters at nadir.

**Stable Disease (SD):** Neither sufficient shrinkage to qualify for PR nor sufficient increase to qualify for PD, taking as reference the smallest sum of the diameters while on study.

**Progressive Disease (PD):** At least a 20% increase in the sum of diameters of all target and all new measurable lesions, taking as reference the smallest sum on study (this includes the baseline sum if that is the smallest on study). In addition to the relative increase of 20%, the sum must also demonstrate an absolute increase of at least 5 mm.

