#### **Impact of New Lesions on Modified RECIST**

New lesions alone do not qualify as progressive disease. However, their contribution to total tumor burden is included in the sum of the diameters, which is used to determine the overall modified RECIST tumor response.

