4.4.2.2 Progression-Free Survival

Progression-free survival (PFS) is determined separately on disease status using RECIST v1.1 and modified RECIST, both evaluated by the investigator.

The date of disease progression is derived based on scan/assessment or death dates, not on visit dates. RECIST assessments/scans contributing towards a particular visit may be performed on different dates.

Progression-Free Survival based per RECIST v1.1 assessments:

PFS is defined as date of first occurrence of tumor progression (earliest of the dates of the RECIST component indicating tumor progression) or date of death (in the absence of tumor progression) by any cause or date of censoring, whichever occurs first, minus date of start of study treatment + 1.

For patients not known to have had a tumor progression or died, the date of censoring is the latest date of assessment from their last evaluable RECIST assessment or the date of start of subsequent cancer therapy whichever occurs first. Patients who never received treatment are censored with time equal to 1 day.

If a patient has no evaluable post-screening RECIST assessments, the patient is censored at the day of study treatment initiation unless the patient dies within 18 weeks. In the latter case, the death date will be used as the date of disease progression.

Progression-Free Survival based per modified RECIST assessments:

PFS according to modified RECIST is defined as:

- date of first occurrence of tumor progression after a modified confirmed response if the patient is a responder according to modified RECIST or
- date of first occurrence of tumor progression in case the patient is not a responder according to modified RECIST or
- date of death (in the absence of tumor progression) by any cause or
- date of censoring, whichever occurs first, minus date of start of study treatment + 1.

For patients not known to have had a tumor progression or died after that modified response, the date of censoring is the latest date of assessment from their last evaluable RECIST assessment or the date of start of subsequent cancer therapy whichever occurs first. Patients who never received treatment are censored with time equal to 1 day.

If a patient has no evaluable post-screening RECIST assessments, the patient is censored with time equal to 1 day unless the patient dies within 18 weeks. In the latter case, the death date will be used as the date of disease progression.

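### Modified-RECIST PFS has no workable progression rule for eligible patients with no target lesion: growth of their existing disease never counts, so their progression may be missed or dated late

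*Protocol*

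**What the plan says.** Protocol 4.1.1, criterion 5, sets the population: "Patients with measurable and/or non-measurable disease according to RECIST v1.1 are allowed". Appendix 2 classes effusions, ascites, peritoneal spread and blastic bone lesions as nonmeasurable, so a patient can enter with no target lesion.

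Appendix 2 then defines progression under modified RECIST:

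- Nontarget lesions contribute to complete response only "and will not be used to assess progressive disease".
- The Summary of Changes entry for radiographic progression reads "Determined only on the basis of measurable disease".
- PD is "At least a 20% increase in the sum of diameters of all target and all new measurable lesions", taken against the smallest sum on study, and "the sum must also demonstrate an absolute increase of at least 5 mm".
- On new lesions: "New lesions alone do not qualify as progressive disease". However, "New measurable lesions are added into the total tumor burden and followed". New lesion types that could not have served as targets are left out of the evaluation.
- The timepoint-response table is stated to be for patients with measurable baseline disease. Appendix 3 (RECIST v1.1) has a Table 2 for nontarget-only patients; Appendix 2 has no counterpart.

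Under SAP 4.4.2.2, the progression date in modified-RECIST PFS for a non-responder is the "date of first occurrence of tumor progression in case the patient is not a responder according to modified RECIST"; death is also an event. SAP 4.1.5 makes ITT the efficacy population. Protocol 6.5 attaches a measurable-disease condition to the response rate, but not to PFS. SAP 4.4.4 plans no sensitivity analyses.

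**The concern.** Criterion 5 lets in patients for whom the modified-RECIST definition of progression was not written. Their known disease can grow unequivocally, in bone, pleura or peritoneum, without producing PD under Appendix 2. The PFS analysis neither excludes them nor gives them a rule of their own.

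Two things are at stake. First, modified-RECIST PFS would combine two endpoints: progression or death in patients with target lesions, and a less sensitive version of it in the rest. Second, modified RECIST exists to accommodate pseudo-progression (Protocol 3.3.7), so a longer PFS than under RECIST v1.1 is likely to be read as benefit beyond apparent progression. Part of that gap could instead come from real progression that was not scored.

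**Working it through.** The plan states no figure that depends on this rule, so there is none to reproduce. The check is a comparison of definitions, one piece of arithmetic, and an illustration of size.

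**1. A patient with no target lesion, under each set of criteria**

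| Finding on scan | RECIST v1.1 (Appendix 3) | Modified RECIST (Appendix 2) |
|---|---|---|
| Unequivocal growth of nontarget disease | PD | Not PD |
| New non-measurable lesion | PD | Not PD |
| New measurable lesion | PD | Counts in the sum; see step 2 |

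**2. Can a new measurable lesion give PD from a zero sum?**

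The baseline sum is 0 mm because there is no target lesion. The smallest measurable new lesion is 10 mm, or 15 mm in short axis for a node.

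- Absolute test: 10 − 0 = 10 mm, or 15 − 0 = 15 mm. Both exceed 5 mm.
- Relative test written as a ratio: 10 ≥ 1.2 × 0 = 0, so it is met.
- Relative test written as a percent change: (10 − 0)/0 is undefined, and neither document gives a convention.

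So PD can be reached, but only by this route and only with a convention that someone has to choose.

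**3. Illustrative size**

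Inputs:

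- Share *f* of patients without a target lesion: not given; 5% to 30% assumed.
- True median PFS: 2.4 months, assumed.
- Median OS: 7 to 9 months (Protocol 3.3.6, second-line treatment).
- Exponential times, with the same true PFS in both groups: assumed.

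Hazards per month are λp = ln 2/2.4 = 0.289 for true PFS, and λo = ln 2/7 = 0.099 or ln 2/9 = 0.077 for death. Affected patients have hazard λa = λo + c(λp − λo), where c is the fraction of the excess progression hazard that is still captured. The apparent median *t* solves

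(1 − f)·exp(−λp·t) + f·exp(−λa·t) = 0.5.

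With f = 10%, OS 7 months and c = 0, t = 2.62 gives 0.422 + 0.077 ≈ 0.50. With c = 0.5, λa = 0.194 and t = 2.49 gives 0.438 + 0.062 = 0.50.

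Apparent median PFS in months (the range is over OS 7 to 9 months):

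| Share | None captured (c = 0) | Half captured (c = 0.5) | All captured (c = 1) |
|---|---|---|---|
| 5% | 2.50–2.52 | 2.44–2.45 | 2.40 |
| 10% | 2.62–2.65 | 2.49–2.50 | 2.40 |
| 20% | 2.87–2.96 | 2.59–2.61 | 2.40 |
| 30% | 3.16–3.33 | 2.69–2.73 | 2.40 |

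The first column is a ceiling, since step 2 shows that new measurable lesions do count. The last column is what results if v1.1 progression is counted. With a longer true median the effect is relatively smaller: at 6.0 months, c = 0 gives 6.05 to 6.74 over the same shares.

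**The case against.** The best defence has four parts.

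- **The fallback.** Appendix 2 defers to RECIST v1.1 where it is silent. Its timepoint table covers measurable disease only, so nontarget-only patients are arguably in that silence and Appendix 3 Table 2 would apply. This is a fair reading, but the sentence on nontarget lesions is not silent: it excludes them from PD without qualification. The fallback does not clearly override it.
- **The SAP wording.** SAP 4.4.2.2 does not mention the sum-only rule. SAP 4.4.2.3 and 4.4.2.4 treat the modified version mainly as looking past progression that precedes a confirmed response. Read that way, a non-responder has the same progression date under both criteria and nothing is biased. This reading is open. However, the SAP also says that PFS is determined separately under each set of criteria, and the endpoint is defined by modified-RECIST status, so the text does not settle it.
- **Not-evaluable scans.** If these patients' scans are treated as not evaluable, SAP 4.4.2.2 censors them at day 1 unless they die within 18 weeks. They then largely leave the risk set.
- **Weight.** This is a descriptive single-arm safety study, and the affected analysis is one of two versions of a secondary endpoint. That limits the importance, not the validity, of the point.

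A reader might go further and infer that these patients can never be scored as progressing, leaving death as their only event. Appendix 2 does not support this, because a new measurable lesion enters the sum. Nor is the bias necessarily upward: that depends on these patients staying at risk, and the not-evaluable route works differently. Nor do the documents support predicting which subgroups would look best: no subgroup in SAP 4.4.5 is defined by measurability.

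**Conclusion.** The point holds in a limited form. Under Appendix 2 as written, an eligible patient with no target lesion cannot progress through existing nontarget disease or new non-measurable lesions. Only a new measurable lesion can give PD, through a percent change that has no defined value. SAP 4.4.2.2 analyses these patients without resolving this, so the same patient could be progressed, progression-free or censored at day 1 depending on an unstated programming choice.

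If Appendix 2 is followed literally and the patients stay at risk, modified-RECIST PFS tends to be overstated. The amount is unknown. At an assumed 10% share and 2.4-month true median, the shift is roughly 0.1 to 0.25 months (2.49 − 2.40 = 0.09; 2.65 − 2.40 = 0.25), and it is zero if v1.1 progression is what the SAP means. These figures depend on the assumed share, true median and exponential times, and only the OS range comes from the documents. RECIST v1.1 PFS already scores nontarget progression and is unaffected. The change is worth making because the explicit rule gives the wrong status for a group that the protocol deliberately admits.

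**What to change.** In SAP 4.4.2.2, add one of two rules for patients with no target lesion at baseline:

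1. Take the modified-RECIST progression date from RECIST v1.1, Appendix 3 Table 2 (unequivocal nontarget progression or a new lesion), keeping the SAP's existing handling of progression before a confirmed response; or
2. Restrict modified-RECIST PFS to patients with measurable disease at baseline, and keep RECIST v1.1 PFS in all patients.

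Apply the chosen rule to the end of response in SAP 4.4.2.4 as well. Report the number of patients affected in either case.

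The cost is a short SAP text change and one derivation. No new data are needed, because Protocol 4.5.5 already has the investigator assess response under both criteria. The downside is that modified-RECIST PFS may be slightly shorter under rule 1, or rest on slightly fewer patients under rule 2.
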